### i. LIST OF ABBREVIATIONS

Define all unusual or 'technical' terms related to the trial. Add or delete as appropriate to your trial. Maintain alphabetical order for ease of reference.

AE	Adverse Event
CI	Chief Investigator
CTU	Clinical Trials Unit
GCP	Good Clinical Practice
GMP	Good Manufacturing Practice
ICF	Informed Consent Form
ISRCTN	International Standard Randomised Controlled Trials Number
NHS R&D	National Health Service Research & Development
PI	Principal Investigator
PIC	Participant Identification Centre
PIS	Participant Information Sheet
QA	Quality Assurance
QC	Quality Control
RCT	Randomised Control Trial
REC	Research Ethics Committee

SAE

Serious Adverse Event

SOP

Standard Operating Procedure

TMG

Trial Management Group

TSC

Trial Steering Committee

**ii. FUNDING AND SUPPORT IN KIND**

FUNDER(S)	FINANCIAL AND NON-FINANCIAL SUPPORT GIVEN
JP Moulton Foundation [name] [name]	£265,272.00

**iii. ROLE OF TRIAL SPONSOR AND FUNDER**

**Trial Sponsor:** The sponsor takes overall responsibility for the initiation, management and financing (or arranging the financing) of the research and must satisfy itself that appropriate arrangements are in place for management, monitoring and reporting of research activity. It is recognised that the sponsor can delegate specific responsibilities to any other individual or organisation where it is appropriate to do so. The University of Exeter undertakes to act as sponsor for the study.

**Funder:** The funder supports the financial requirements of the trial but has no role in the design, delivery or dissemination of the study. The research team will honour the Terms and Conditions of the funder, JP Moulton Foundation.

**iv. ROLES AND RESPONSIBILITIES OF TRIAL MANAGEMENT COMMITTEE***Trial Management Group*

The Trial Management Group will meet annually, with six-monthly teleconference to oversee the trial. Membership will consist of an independent statistician and two experts in the field. The TMG will have authority to end the trial early and will review any adverse events. A sub-group of the TMG will meet monthly to oversee the running of the trial and to coordinate interim reports from the study coordinator.

**v. KEY WORDS:**

Vitamin D, online, Age-Associated Cognition Decline, Cognition, RCT

[figure not shown]
**vi. TRIAL FLOW CHART***CONSORT Chart*

The CONSORT chart below shows the proposed flow of participants through this study.

IRAS ID: 247136

Protocol version: 8.0

Date: 5th May 2023

## 1 BACKGROUND

Dementia is a devastating condition that affects over 820,000 people in the UK. It is characterised by the gradual loss of brain function which causes symptoms such as memory loss, changes in behaviour and difficulties with language. Dementia leads to loss of mobility, communication and independence, and eventually to death. Apart from the enormous emotional and personal impact, dementia exerts a considerable financial cost across society. This includes an additional substantial cost to individuals and their families who provide informal care for their loved ones, as well as an estimated cost of £26.3 billion each year to the UK health service. Worldwide this figure reaches US\$818billion.

While research continues to search for effective treatments there is increasing pressure to establish approaches to reduce the risk of cognitive decline and dementia, particularly in high risk groups who already have some degree of cognitive impairment. Cognitive decline is common amongst older adults. Whilst a degree of cognitive loss, or 'slowing down' of brain function, is a normal part of healthy ageing, it can also be a precursor to dementia. These more subtle forms of cognitive decline such as Mild Cognitive Impairment (MCI) are common in older adults. Between 5 and 10% of people with MCI develop dementia each year, making them a high risk group. Even more common is an earlier form of impairment known as Age-Associated Cognitive Decline (AACD). AACD is defined by subtle changes in key abilities, particularly problem-solving and memory, which indicate early changes in the brain that may lead to more severe changes later in life. AACD can be detected in people who are otherwise completely healthy and functioning normally in daily life. There is no current diagnostic or treatment pathway for people with AACD, despite their high risk of developing dementia. Treatment for AACD is therefore a huge unmet need. Other key risk factors for the development of dementia later in life include a recorded family history of dementia in close family members and the recognition of subjective concerns of memory loss or cognitive change. An approach that reduced risk of further decline would be an enormously powerful way of minimising dementia risk across a large sector of the population.

Reducing risk of dementia is now a major public health issue, and it has been highlighted in UK government strategy as well as by global health organisations. The potential impact of a strategy to preserve cognition and delay the onset of dementia symptoms, even by a few months, could have a significant impact at a population level, and improve the health and wellbeing of older adults across the UK. There is emerging evidence that prevention is a realistic way to reduce the burden of dementia which could result in improvements to society and individuals in the next decade. There is also good evidence to support a number of different approaches for reducing the risk of dementia, of which one of the most promising is supplementation of key dietary elements. There is good agreement amongst experts in the field that the most effective way to approach prevention is to tailor treatments to the needs of different groups rather than attempt a catch-all approach, due to the extreme complexity of cognitive health. This study therefore takes a 'precision medicine' approach and targets a specific, high priority group of at-risk individuals.

## 2 RATIONALE

A promising avenue for dementia risk reduction is through supplementation of dietary deficiencies, particularly with Vitamin D. A rapidly growing body of evidence strongly indicates that Vitamin D may play a role in brain health and cognition. We first identified Vitamin D as a potential intervention for dementia prevention in 2009 when we published the first large population study linking low vitamin D levels in 1,766 English older adults to cognitive impairment. This was of considerable concern as a large proportion of older adults are vitamin D deficient. Vitamin D receptors are found throughout the brain, and they are now thought to have several precognitive and neuroprotective effects. For example, vitamin D reduces the hallmarks of Alzheimer's disease including amyloid beta and phosphorylated tau. We conducted the first large prospective study establishing that severe vitamin D deficiency (<25 nmol/L) increases the risk of substantial cognitive decline over six years by around 60%. People with severe deficiency are around 120% more likely to develop dementia over a six-year period. These landmark studies have been replicated by other groups and confirmed in a series of systematic reviews and meta-analyses. Related animal studies have also been highly encouraging. For example, supplementing middle-aged rats for six months prevented cognitive decline and promoted hippocampal synaptic function. If confirmed to be protective against dementia in humans, this would represent a major breakthrough that would have enormous impact worldwide.

Taken together this evidence presents a compelling case to suggest that vitamin D supplements may reduce cognitive decline and delay or even prevent the onset of dementia. The supplements are known to be safe for older adults, are very affordable and widely available. Uptake of dietary supplements is limited however, perhaps due to a lack of clear evidence from clinical trials. Indeed, analysis of a cohort of over 9000 people revealed that only 11.8% of people report taking any supplements. In spite of the robust supporting evidence there have been no large clinical trials of Vitamin D in people at risk of dementia. This study seeks to address this gap and to conduct a definitive trial to determine whether

Vitamin D supplementation is an effective means of reducing risk of cognitive loss in people with AACD. The study will focus on people who are also at risk of Vitamin D deficiency in order to target the treatment to an appropriate group.

This study will be delivered through the existing online PROTECT cohort. PROTECT is an online cohort of >20,000 adults aged 50 and over who complete annual assessments of cognition, health and wellbeing. PROTECT is also an online clinical trials platform ([www.protectstudy.org.uk](http://www.protectstudy.org.uk)), offering automated data collection and identification of eligible participants. The large, fully characterised PROTECT cohort, all of whom have provided consent for contact, offers a tailor-made recruitment source for clinical trials.

## 2.1 Assessment and management of risk

The medication to be tested in this trial is a dietary supplement, not presented as a medicine, in a dose already available to the public. As per the [MHRA guidance](#) the intervention is not a medicinal product and thus this trial is not classified as a CTIMP.

## 3 OBJECTIVES AND OUTCOME MEASURES/ENDPOINTS

This trial aims to establish the impact of dietary supplementation with Vitamin D on cognition and day-to-day function in at-risk older adults with vitamin D deficiency and Age-Associated Cognitive Decline (AACD), subjective memory concerns and / or family history of dementia.

### 3.1 Primary Research Question

Can Vitamin D supplementation result in benefits to executive function in adults with dementia risk and vitamin D deficiency over two years (Primary Outcome)?

### 3.2 Secondary Research Questions

1. Can Vitamin D supplementation result in benefits to cognitive functioning in adults with dementia risk and vitamin D deficiency over two years (Secondary Outcome)?
2. Can Vitamin D supplementation result in benefits to day-to-day functioning in adults with dementia risk and vitamin D deficiency over two years (Secondary Outcome)?

### 3.3 Outcome measures/endpoints

All outcome measures will be collected at six, 12, and 24 months.

### 3.4 Primary endpoint/outcome

The primary outcome measure will be Trails B as measured through the PROTECT online test battery. This measure has been used to assess cognitive change in adults with dementia risk extensively in the literature (e.g. Park 2022, Kim et al 2021).

### 3.5 Secondary endpoints/outcomes

Additional secondary outcome measures will be cognitive domains measured by the cognitive test battery (Paired Associate Learning, Digit Span, Self-Ordered Search Task [working / spatial memory tasks], Switching Stroop and Grammatical Reasoning [Executive Function Tasks]) and day-to-day functioning as measured by the well-validated Instrumental Activities of Daily Living Scale. Cost-effectiveness of the Vitamin D treatment will be measured through the widely adopted EQ5D scale. All assessments will be carried out online through the PROTECT study. Cognitive measures will be completed in one session to reduce the burden on the participant. At the end of the study an anonymous online survey will be completed to capture participant experience of the study.

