### 3.7 Table of endpoints/outcomes

Objectives	Outcome Measures	Timepoint(s) of evaluation of this outcome measure (if applicable)
Primary Objective To compare the effect of vitamin D supplementation on executive function	Trails-B measure, completed in one session online on the PROTECT website.	Baseline, six, 12, and 24 months Primary endpoint is 24 months
Secondary Objectives To compare the effect of vitamin D supplementation on cognition, function and behaviour  To establish the cost-effectiveness of vitamin D supplementation	Cognitive Test Battery (Paired Associate Learning, Digit Span, Self-Ordered Search Task [working / spatial memory tasks], Switching Stroop and Baddeley Grammatical Reasoning [Executive Function Tasks  Instrumental Activities of Daily Living Scale  Mild Behaviour Impairment Scale  EQ5D scale	Baseline, six, 12, and 24 months
Tertiary Objectives Example: To monitor safety and compliance of vitamin D supplementation in the trial cohort  To explore participant experience of taking part in an online trial	Adverse Event and Serious Adverse Event reporting in response to email prompts, or proactively by participants through the website, telephone or email  Anonymous survey	Quarterly  24 months (after study completion)

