### 7.6 Baseline data

Participant data will be pulled from the PROTECT main dataset to populate the baseline data point. This will include:

- Age
- Gender
- Education level
- 
- Use of brain training games prior to randomisation (not an eligibility or randomisation factor – for use in analysis only)
- Lifestyle factors as captured by the PROTECT lifestyle questionnaire (not an eligibility or randomisation factor – for use in analysis only)

Cognitive Assessment data and all other trial-specific measures will be collected within the trial areas as part of the scheduled assessment at baseline.

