### 7.7 Trial assessments

Assessments will be conducted at baseline, 26, 52, and 104 weeks. Participants will receive weekly automated emails notifying them that assessments are available to complete until they are completed or no longer available. The assessments will become available for completion two weeks before the assessment point and remain open for completion during the week of the assessment point and a further five weeks, making them available for eight weeks in total. Missing data or late data will be accounted for within the analysis plan.

Assessments will follow the set online assessment protocol described below.

1. scale Trail-making B (primary outcome measure)
2. PROTECT Cognitive Tests: Switching Stroop Test, Baddeley Grammatical Reasoning , Self-ordered Search, Digit Span, and Paired Associate Learning Tasks (secondary outcome measures)
3. Instrumental Activities of Daily Living
4. EQ5D measure of health and wellbeing
5. Mild Behaviour Impairment Scale

An anonymous survey will be completed at the end of the study to provide a process measure and to capture participant experience.

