### 8.11 Assessment of compliance with treatment

**Compliance Monitoring:** Monitoring of participant use of the tablets will be achieved through a 'medication diary' on the PROTECT site which will ask participants to provide a quarterly tablet count, both of which will be entered online. This will also be supported through reminder emails and regular newsletters from the PROTECT study. This process is anticipated to be highly effective. However, since it is reliant on participant adherence and fidelity, an additional sub-group of compliance testing will also be performed (see below).

**Sub-group Compliance Monitoring:** In addition a sub-group of 10% of the total cohort (n = 58) will be recruited to complete a finger prick test to analyse blood levels of Vitamin D3 metabolites at baseline and primary endpoint (24 months) as a further compliance measure. This process will be delivered through partnership with the Sandwell and West Birmingham NHS foundation Trust test facility. This process will involve:

- Sub-group compliance participants allocated to the first 10% of randomised participants
- Study administrator attaches participant identifier label to test kit and posts kit to participant
- Participants will receive a test kit to complete at home, involving a short finger prick test
- Participants use pre-addressed envelope to send their completed test to the Sandwell and West Birmingham NHS Foundation Trust test laboratory
- Laboratory completes Vitamin D3 analysis according to published protocols using anonymised sample identifiers. No sample is retained after analysis
- Laboratory returns anonymised test results to study team

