## 9.2 Operational definitions for (S)AEs

### *Adverse Event*

An AE is defined as any medical event occurring to a participant during the two-year study that requires medical intervention.

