### *Serious Adverse Event*

An SAE must fulfil the following criteria:

- Hospitalisation, excluding admission for scheduled and elective surgery
- Death
- Life-threatening condition, excluding conditions already in an unstable state at registration

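### Sections 3.5 and 3.7 promise cost-effectiveness, but EQ5D gives only the effect side and no resource-use or cost instrument is scheduled

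*Protocol*

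**What the plan says.** The table in Protocol section 3.7 gives as a secondary objective "To establish the cost-effectiveness of vitamin D supplementation". Of the measures beside it, only EQ5D could serve that purpose, and section 3.5 makes the link explicit: "Cost-effectiveness of the Vitamin D treatment will be measured through the widely adopted EQ5D scale".

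Section 7.7 introduces its list with "Assessments will follow the set online assessment protocol described below". The list has five items: Trails B, the PROTECT cognitive tests, the daily-living scale, EQ5D and the Mild Behaviour Impairment Scale. There EQ5D is called an "EQ5D measure of health and wellbeing". Baseline data in section 7.6 are demographics, education, prior brain-training use and "Lifestyle factors as captured by the PROTECT lifestyle questionnaire".

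Section 10.3 compares primary and secondary outcomes between arms and names no economic analysis.

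**The concern.** A cost-effectiveness result is a statement about two differences between arms, one in health and one in cost. Section 3.5 assigns the whole of it to an instrument that measures health only. The protocol's own description of EQ5D in section 7.7 agrees with that narrower role.

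This is a matter for the protocol. A statistical or health-economic analysis plan can settle the perspective, unit prices, value set and QALY calculation, and their absence here is no fault. Such a plan cannot create participant-level service use that the trial did not schedule for collection.

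At stake is what the trial may conclude. With the objective worded as it is, an EQ5D difference could be presented as evidence on cost-effectiveness, or a cost per QALY could rest on little more than the price of the capsules without the reader being told.

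**Working it through.** No figure in the protocol has to be reproduced. The check is to write down what a cost-effectiveness comparison needs and to look for each part in the data collection.

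**Quantities needed.** With ΔE the between-arm difference in mean QALYs, ΔC the difference in mean cost and λ a value per QALY:

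- cost per QALY = ΔC / ΔE
- incremental net benefit = λ·ΔE − ΔC

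Both forms need ΔC.

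**Effect side, ΔE.** EQ5D is scheduled at baseline and at 26, 52 and 104 weeks, that is at 0, 0.5, 1 and 2 years. By the trapezium rule:

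QALY = 0.5·(u0 + u0.5)/2 + 0.5·(u0.5 + u1)/2 + 1·(u1 + u2)/2 = 0.25·u0 + 0.5·u0.5 + 0.75·u1 + 0.5·u2

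The weights sum to 0.25 + 0.5 + 0.75 + 0.5 = 2 years. QALYs over 24 months can thus be obtained from the schedule, once a value set is chosen.

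**Cost side, ΔC.** The components of a health-and-care perspective, set against what the protocol collects:

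| Component | Nearest data | Status |
|---|---|---|
| Intervention | Dispensing records (8.5); participants also "provide a quarterly tablet count" (8.11) | Quantity available: 104 × 7 = 728 daily capsules, or 728 / 28 = 26 packs if fully supplied. No price is given in the protocol |
| Unplanned admissions and treated events | Adverse-event reports (9.2, 9.3) | Partly available |
| Routine health-service use | No dedicated item in 7.6, 7.7 or 9.3 | Not scheduled |
| Social care | None | Not scheduled |
| Informal care | None | Not scheduled |

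**How far the adverse-event records go.** Section 9.2 states: "An AE is defined as any medical event occurring to a participant during the two-year study that requires medical intervention". Its serious-event criterion is "Hospitalisation, excluding admission for scheduled and elective surgery". Section 9.3 has participants report online, with a prompt each quarter, and records the description, the duration, what was done and the outcome. From this one could count and date unplanned admissions and treated events by arm.

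Three limits remain. Planned surgical admissions fall outside the serious-event definition. The records are self-reported events, with no field for the number of visits, bed-days or care hours as such. And no section ties them to the economic objective.

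Of the five components, one is available in quantity, one in part and three are not scheduled.

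**The case against.** The best reply is that the cost side is not empty. Dispensing records and tablet counts allow the intervention to be costed once a price is supplied. Adverse-event reports run from the start of treatment to the end of the trial, carry dates and include unplanned hospitalisation. They are participant-level and can be compared by arm. This stands. A reader might infer that no cost or resource-use data exist, that the cost difference is unobserved for all 584 participants, or that the objective cannot be met in any form. The documents do not support any of these. A narrow cost per QALY, based on intervention cost and perhaps event costs, remains possible.

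A second reply is that the trial sits inside the PROTECT cohort, which assesses health and wellbeing every year (section 2), and that section 11.1 points to specification documents not shown here. Service use might be recorded there. The protocol does not say that it is, and section 7.6 draws no such item from the cohort. The possibility stays open but does not rescue the wording of section 3.5.

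Third, it would be a prediction to say that the trial will report an EQ5D difference as cost-effectiveness, because section 10.3 describes no economic reporting. Nor does section 1 rank care costs as the main burden: it describes costs of dementia to families and to the health service. People with diagnosed dementia are excluded, so the documents do not establish how large a two-year care-cost effect might be in this population.

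Last, cost-effectiveness is not among the two secondary research questions in section 3.2. That limits the weight of the point. It also means that restating the objective removes no question posed there.

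**Conclusion.** The point holds in a limited form. Section 3.5 misdescribes EQ5D: it supplies utilities and QALYs, not cost-effectiveness. No resource-use or cost instrument is scheduled in 7.6 or 7.7, and the compliance and safety records fill only part of the gap. As scheduled, the trial cannot establish cost-effectiveness from a health-and-care perspective, although it can estimate QALYs and a narrow, intervention-based cost per QALY.

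In size, this is one of the two secondary objectives in section 3.7. The primary endpoint, randomisation, sample size and safety reporting are not affected.

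The conclusion assumes that sections 7.6, 7.7, 8.5, 8.11 and 9.2 to 9.3 describe all the trial data relevant to costs. If the host cohort also records service use for these participants over the same period, the protocol should say so, and the conclusion would soften.

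**What to change.** In sections 3.5 and 3.7, replace cost-effectiveness with *health-related quality of life (EQ5D) and QALYs over 24 months*. Add one sentence: any cost-per-QALY figure is exploratory and limited to intervention cost, plus event costs from the adverse-event records if these are used.

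This needs no new data and leaves the primary analysis as it is. The costs are a less ambitious secondary objective and a protocol amendment through the route in section 13.10.

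Adding a resource-use recall to the remaining online assessments may look attractive but is not advised. Version 8.0 comes late in the trial: Appendix A reports that power for the two-year outcome had already been reached. A recall begun now would cover only a late and selected part of follow-up.
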